## Comedications

Comedications will be ascertained through medication codes recorded in the 6 months before the start date.

Note: The Anatomical Therapeutic Chemical (ATC) codes in Table 5 will be mapped to Multilex/British National Formulary codes.

**Table 5. Anatomical Therapeutic Chemical Codes for Comedications**

Disease Description	ATC
Cardiovascular medications	C
Cardiac glycosides	C01A
Antiarrhythmics, Class I and III	C01B
Cardiac stimulants excluding cardiac glycosides	C01C
Vasodilators used in cardiac diseases	C01D
Other cardiac preparations	C01E
Diuretics	C03
Peripheral vasodilators	C04
Pentoxifylline	C04AD03
Beta blocking agents	C07

Disease Description	ATC
Calcium channel blockers	C08
Antihypertensives	C02
Agents acting on the renin-angiotensin system	C09
Angiotensin-converting-enzyme inhibitors	C09A, C09B
Angiotensin II receptor antagonists	C09C, C09D
Renin-inhibitors	C09X
Lipid-modifying agents	C10
Statins	C10AA
Simvastatin	C10AA01
Lovastatin	C10AA02
Other lipid-modifying agents	C10AB, C10AC, C10AD, C10AX, C10BA
Statin combinations with ASA	C10BX
Antithrombotic agents	B01
Platelet aggregation inhibitors	B01AC
Clopidogrel	B01AC04
Acetylsalicylic acid	B01AC06, B01AC30, B01AC56
Other platelet aggregation inhibitors	B01AC01-B01AC03, B01AC05, B01AC07-B01AC22, B01AC24
Vitamin K antagonists	B01AA
Heparins	B01AB
Other antithrombotic agents	B01AD, B01AE, B01AX
Iron preparations	B03A
Proton pump inhibitors	A02BC
Omeprazole	A02BC01
Drugs used in diabetes	A10
Insulins	A10A
Blood glucose lowering drugs	A10B, A10X
Drugs for obstructive airway diseases	R03
Drugs for musculoskeletal system	M01A, N02BA, M01B, M01C
Non-steroidal anti-inflammatory drugs	M01A
Acetylsalicylic acid (other analgesics and antipyretics)	N02BA
Other antirheumatic agents	M01B-M01C
Antidepressants	N06A
Selective serotonin reuptake inhibitors	N06AB
Antineoplastic agents	L01
Immunosuppressants	L04
Antivirals for systemic use	J05
Other medications	
Systemic corticosteroids	H02

Disease Description	ATC
Hormone replacement therapy	G03C, G03D, G03F
Drugs used in nicotine dependence	N07BA

ATC = Anatomical Therapeutic Chemical.

### 9.3.4 Concurrent Use of Medications That May Interact With Cilostazol

Cilostazol is extensively metabolised by cytochrome P-450 (CYP450) enzymes, particularly CYP3A4 and to a lesser extent by CYP2C19. Medications potentially interacting with cilostazol are listed in the risk management plan and in the summary of product characteristics and include CYP3A4 and CYP2C19 substrates and inhibitors and CYP3A4 inducers. A summary of these medications is presented in Table 6. A complete list of clinically relevant medications interacting with CYP450 is presented in Annex 3.

**Table 6. Medications Potentially Interacting With Cilostazol**

Medication	Substrates		Inhibitors		Inducers
	CYP2C19	CYP3A4	CYP2C19	CYP3A4	CYP3A4
Proton pump inhibitors					
Lansoprazole	X		X		
Omeprazole	X		X		
Antiepileptics					
Phenytoin	X				X
Carbamazepine					X
Macrolide antibiotics					
Clarithromycin		X		X	
Erythromycin		X		X	
Protease inhibitor antivirals					
Indinavir		X		X	
Ritonavir		X		X	
Nelfinavir				X	
Gastrointestinal					
Cisapride		X			
Calcium channel blockers					
Diltiazem		X		X	
Statins					
Simvastatin		X			
Antimycotics					
Ketoconazole			X	X	
Itraconazole				X	
Antimycobacterials					
Rifampin					X

Medication	Substrates		Inhibitors		Inducers
	CYP2C19	CYP3A4	CYP2C19	CYP3A4	CYP3A4
Antipsychotics					
Pimozide		X			

CYP = cytochrome P-450.

For each user of cilostazol, the use of each medication listed in Annex 3 will be ascertained at the start date and during follow-up for current use of cilostazol (Section 9.3.1).

- Concurrent use at the start date:
  - Patients who have at least one prescription for a potentially interacting medication recorded within 3 months before the start date
- Concurrent use during follow-up:
  - Patients who have at least one prescription for a potentially interacting medication recorded during the time of current use of cilostazol.
  - Patients who have at least one prescription for a potentially interacting medication recorded during the time of consecutive use of cilostazol as defined in Section 9.3.1 (duration of use of cilostazol).

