**Variables:**

*Use of cilostazol and patterns of use:* The number of new users of cilostazol and the number of prescriptions, packages, and defined daily dose (DDD) will be ascertained overall and by strength, quantity, and year. Current use of cilostazol will be ascertained according to the days of supply of each prescription for cilostazol.

- *Duration of use of cilostazol:* Total duration of use of cilostazol will be ascertained by the total number of days of supply of consecutive prescriptions.
- *Daily dose of cilostazol:* Daily dose of cilostazol will be calculated using the recorded information on strength and quantity prescribed and the days of supply of each prescription.

*Characterisation of users at the start date:* New users of cilostazol will be characterised at the start date according to demographic, family history, comorbidity, and comedications.

*Concurrent use of medications that may interact with cilostazol:* Use of medications potentially interacting with cilostazol, including potent inhibitors of CYP3A4 and CYP2C19, will be ascertained at the start date, in the 3 months before the start date, and in the follow-up during current use of cilostazol.

*Concurrent use of selected antithrombotic agents:* The concurrent use of cilostazol with platelet aggregation inhibitors and antithrombotic agents will be ascertained at the start date and during follow-up. Use of each antithrombotic agent will be defined according to the days of supply of each prescription. The number of patients simultaneously contributing time to current use of cilostazol and current use of antithrombotic agents at the start date and during follow-up will be ascertained.

*Use of platelet aggregation inhibitors:* New users of cilostazol concurrently treated with platelet aggregation inhibitors at the start date will be followed to assess the proportion of patients discontinuing the use of platelet aggregation inhibitors.

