#### 9.3.4.1 Concurrent Use of Potent Inhibitors of CYP3A4 and CYP2C19

Concurrent use of potent inhibitors of CYP3A4 and CYP2C19 will also be evaluated. Potent inhibitors are those identified as such by the Indiana Classification (Trustees of Indiana University, 2013) and the United States Food and Drug Administration Drug Development and Drug Interactions website. Potent inhibitors are lansoprazole, fluvoxamine, nefazodone, ticlopidine, clarithromycin, troleandomycin, indinavir, ritonavir, nelfinavir, mibefradil, ketoconazole, and itraconazole.

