### **9.3.5 Concurrent Use of Selected Antithrombotic Agents**

In addition to potentially interacting drugs, the concurrent use of cilostazol with platelet aggregation inhibitors and antithrombotic agents will be assessed. Antithrombotic agents are listed in Table 5.

Use of each antithrombotic agent will be defined, similarly to cilostazol use, according to the days of supply of each prescription. If days of supply of prescriptions are not recorded in some databases, they will be estimated from descriptive analysis of the number of days between consecutive prescriptions. Current use of each antithrombotic agent is defined as the time involving the days of supply of each prescription plus 7 days to allow for a potential delay in the start of treatment.

Concurrent use of cilostazol and antithrombotic agents will be ascertained as follows:

- At the start date:
  - Use of antithrombotic agents at the start date will be ascertained according to the days of supply of the most recent prescription for each antithrombotic agent before the start date (date of first prescription for cilostazol).
- Overall:
  - Patients simultaneously contributing time to consecutive use of cilostazol and current use of antithrombotic agents at the start date and during follow-up.

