**Table 7. Proposed Changes in the Labelling of Cilostazol and Characterisation of Users**

Proposed Change to Summary of Product Characteristics	Characterisation in DUS
Restricted target population	
Indication	
4.1 Cilostazol is for second-line use in patients in whom life-style modifications (including smoking cessation and [supervised] exercise programmes) and other appropriate interventions have failed to sufficiently improve their intermittent claudication symptoms	Smoking status a
4.2 The physician should reassess the patient after 3 months of treatment with a view to discontinuing cilostazol where an inadequate effect is observed.	Number of patients seen by the treating physician after 3 months b Number of patients discontinuing after 3 months b
Contraindications	
4.3 Patients with unstable angina pectoris, myocardial infarction within the last 6 months, or a coronary intervention in the last 6 months	Unstable angina Myocardial infarction Coronary intervention
Patients treated concomitantly with two or more additional antiplatelet agents (e.g., aspirin, clopidogrel)	Concurrent use of two or more platelet-aggregation inhibitors
Other SmPC changes	
Warnings and precautions	
4.4 Based on its mechanism of action, cilostazol may induce tachycardia, palpitation, tachyarrhythmia, and/or hypotension. The increase in heart rate associated with cilostazol is approximately 5 to 7 beats per minute; in patients at risk, this may induce angina pectoris.	
Patients who may be at increased risk for serious cardiac adverse events as a result of increased heart rate, e.g., patients with stable coronary disease or a history of tachyarrhythmias, should be monitored closely during the treatment with cilostazol; the use of cilostazol in patients with unstable coronary disease or coronary intervention within the last 6 months is contraindicated (see SmPC Section 4.3).	Number of visits to general practitioner and/or specialist

Proposed Change to Summary of Product Characteristics	Characterisation in DUS
Posology	
4.2 Reduction of the dose to 50 mg twice daily is recommended in patients receiving medicines that strongly inhibit CYP3A4, e.g., several macrolides, azole antifungals, protease inhibitors, or medicines that strongly inhibit CYP2C19, e.g., omeprazole.	Daily dose

CYP = cytochrome P-450; DUS = drug utilisation study; SmPC = Summary of Product Characteristics.

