  - Patients with a history of arrhythmias, hypotension, or coronary heart disease recorded at any time before the start date will be followed to assess the rates of visits to general practitioners or specialists. Visit rates for these patients will be used as a proxy of intensified monitoring and compared with the rates for the patients who do not have a history of arrhythmias, hypotension, or coronary heart disease.
- Posology
  - Daily dose of cilostazol at the start date will be assessed among concurrent users of potentially interacting medications at the start date
  - Reduction of daily dose to 50 mg will be assessed among patients who are prescribed a potentially interacting medication during continuous use of cilostazol.

The diagnosis, procedure, and medication codes that will be used to define the variables for the evaluation of the risk minimisation measures are included in Table 4 and Table 5.

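### Section 9.3.4 counts any interacting prescription from the previous 3 months as concurrent use at the start date, so finished short courses enter Tables 10 and 13 and the starting-dose assessment

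*Protocol*

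**What the plan says.** Section 9.3.4 (text after Table 6) gives one criterion for concurrent use of interacting medication at the start date: "Patients who have at least one prescription for a potentially interacting medication recorded within 3 months before the start date". It sets no condition on days of supply or overlap. The medications concerned "include CYP3A4 and CYP2C19 substrates and inhibitors and CYP3A4 inducers", listed in full in Annex 3.

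Section 9.3.6, under Posology, then uses this group: "Daily dose of cilostazol at the start date will be assessed among concurrent users of potentially interacting medications at the start date". The label text being evaluated, in Table 7, reads: "Reduction of the dose to 50 mg twice daily is recommended in patients receiving medicines that strongly inhibit CYP3A4". It extends to strong CYP2C19 inhibitors.

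Section 9.3.5 follows a different rule for another drug group: "Use of antithrombotic agents at the start date will be ascertained according to the days of supply of the most recent prescription". It adds 7 days to the supply when defining current use, and provides for estimating supply where it is not recorded.

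The abstract (Variables) says interacting use "will be ascertained at the start date, in the 3 months before the start date, and in the follow-up during current use of cilostazol". There the start date and the preceding 3 months are separate items.

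Section 9.7.3 assigns start-date use to Analysis Table 10, use during current and consecutive cilostazol use to Tables 11 and 12, and use at any of these times to Table 13.

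**The concern.** A patient who finished a macrolide or azole course some weeks before the first cilostazol prescription is classed as a concurrent user at the start date. That patient was not receiving the inhibitor when cilostazol was started, so the label text in Table 7 did not bear on the starting dose. The protocol nevertheless counts the patient as co-exposed at initiation and includes the patient in the group whose starting dose is examined.

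Two results are exposed. The first is the prevalence of interacting co-use at initiation (Table 10, carried into Table 13). The second is the starting-dose description in section 9.3.6, one of the items used to judge the risk minimisation measures by comparing DUS2 with DUS1. The limitations in section 9.9 discuss exposure misclassification in general terms but do not mention this source.

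**Working it through.** **No stated figure to reproduce.** The protocol gives no number for interacting co-use, finished courses or starting dose among co-users. The size below therefore rests on stated assumptions.

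**Step 1: which drugs are affected.** Section 9.3.4.1 lists 12 potent inhibitors: lansoprazole, fluvoxamine, nefazodone and ticlopidine, followed by "clarithromycin, troleandomycin, indinavir, ritonavir, nelfinavir, mibefradil, ketoconazole, and itraconazole". Four of these are anti-infectives that may be given as limited courses (my classification): clarithromycin, troleandomycin, ketoconazole and itraconazole. Annex 3 as a whole also contains proton pump inhibitors, statins, calcium-channel blockers and other drugs usually taken long term. For repeat medication the latest prescription normally covers the start date, so the two definitions nearly coincide.

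**Step 2: overlap of a one-off short course.** Assume the course is equally likely to start on any day of a 91-day window. A course of L days, with an allowance of g days, reaches the start date with probability (L + g)/91.

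| Course | Allowance | Overlap | No overlap |
|---|---|---|---|
| 7 days | 0 | 7/91 = 7.7% | 92.3% |
| 7 days | 7 days | 14/91 = 15.4% | 84.6% |
| 14 days | 0 | 14/91 = 15.4% | 84.6% |
| 14 days | 7 days | 21/91 = 23.1% | 76.9% |

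So 77% to 92% of such courses would not overlap. This is a share of one-off short courses, not of the whole denominator.

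**Step 3: effect on starting dose.** Let c be the share on the reduced dose among patients with true overlap, r the share among patients whose course had finished, and f the fraction of the denominator with finished courses. None of the three is in the protocol.

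Observed share = (1 − f)c + f·r

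With c = 50% and r = 10% (assumed):
- f = 5%: 0.95 × 50 + 0.05 × 10 = 48%
- f = 10%: 0.90 × 50 + 0.10 × 10 = 46%
- f = 20%: 0.80 × 50 + 0.20 × 10 = 42%
- f = 40%: 0.60 × 50 + 0.40 × 10 = 34%

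If r = c there is no bias, whatever f is.

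**Step 4: effect on the DUS1–DUS2 contrast.** If f and r are the same in both studies, the f·r term cancels and the observed difference is (1 − f) times the true one. A true rise from 30% to 50% (20 points, assumed) would show as 19, 18, 16 or 12 points for f = 5%, 10%, 20% or 40%.

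**Step 5: which analyses inherit the definition.** Tables 10 and 13 do, as does the starting-dose item in section 9.3.6. Tables 18A and 18B (section 9.7.5) examine dose reduction during continuous use and do not draw on the start-date group. Table 5 gives starting dose by sex and age only.

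**The case against.** The strongest reply is that the 3-month window is disclosed in the abstract and section 9.1, so Table 10 can be read as a look-back count, and that co-use during cilostazol treatment is reported separately in Tables 11 and 12. This stands in part: a finished course that is not repeated does not appear in those two tables. But they count prescriptions recorded during cilostazol use, so a course begun shortly before the start date and still running is missed there too. No table gives overlap at initiation, and the word concurrent invites that reading of Table 10.

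A reader might infer more than the documents support on four counts:

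- **That 77% to 92% of the denominator is not concurrent.** That figure covers only one-off short courses. Annex 3 is largely long-term medication, and f is unknown.
- **That adherence to the label dose is understated and the evaluation biased towards failure.** This needs r below c, which is plausible but nowhere stated. The protocol sets no pass mark, and one rule applied in both studies mainly attenuates the contrast.
- **That the dose analyses in section 9.7.5 are affected.** They are not, as Step 5 shows.
- **That the 9.3.5 rule can simply be substituted.** Where supply is unrecorded, that section estimates it from intervals between consecutive prescriptions. A single course has no such interval, and Table 9 derives duration from prescriptions in four of the five databases. Section 6.1 also reports DUS1 complete in four databases by 30 January 2015, so changing DUS2 alone would break comparability.

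A further point is that substrates and inducers share the denominator, while the quoted label text concerns strong inhibitors. An overlap rule alone would not remove that dilution.

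**Conclusion.** The point holds in limited form. Section 9.3.4 labels a 3-month look-back as concurrent use at the start date. This departs from the overlap rule in section 9.3.5, from the separate listing in the abstract, and from the population that the Table 7 label text describes. Finished short courses therefore enter Tables 10 and 13 and the section 9.3.6 starting-dose assessment.

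The misclassification is concentrated in short-course anti-infectives, where 77% to 92% of one-off 7- to 14-day courses would not overlap under uniform timing. Its effect on the full interacting-drug denominator cannot be derived and is probably small; it may be larger within the potent-inhibitor group. The expected consequence is some overstatement of co-use at initiation and, if patients with finished courses receive the reduced dose less often, attenuation of the DUS1–DUS2 contrast in starting dose.

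**What to change.** 1. In section 9.3.4, keep the 3-month count but label it *recent use (3 months)*. This preserves comparability with DUS1.
2. Add an overlap-based count: days of supply of the most recent interacting prescription, plus 7 days, covering the start date, in line with section 9.3.5. For single courses with unrecorded supply, use a pack-based or assumed duration and vary it in a sensitivity analysis.
3. Report the section 9.3.6 starting-dose result in the overlap group, at least for the potent inhibitors of section 9.3.4.1. This also brings the denominator closer to the label text in Table 7.
4. Reconcile section 9.3.4 with the abstract, and make clear in Tables 10 and 13 which definition each count uses.

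Tables 18A and 18B need no change. The data are already held, and section 7 allows protocol adjustments after DUS1. The costs are an added count in Tables 10 and 13, an assumed duration for some single courses, and re-tabulation of DUS1 if the overlap result is to be compared like for like. Without that re-tabulation, only the 3-month count is comparable between the two studies.

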#### 9.3.4.1 Concurrent Use of Potent Inhibitors of CYP3A4 and CYP2C19

Concurrent use of potent inhibitors of CYP3A4 and CYP2C19 will also be evaluated. Potent inhibitors are those identified as such by the Indiana Classification (Trustees of Indiana University, 2013) and the United States Food and Drug Administration Drug Development and Drug Interactions website. Potent inhibitors are lansoprazole, fluvoxamine, nefazodone, ticlopidine, clarithromycin, troleandomycin, indinavir, ritonavir, nelfinavir, mibefradil, ketoconazole, and itraconazole.

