*Characterisation of users for the assessment of risk minimisation measures (SmPC changes):* Users of cilostazol will be characterised to evaluate the impact of the risk minimisation measures that Otsuka submitted to the EMA in October 2012. For this evaluation, DUS2 is planned to be initiated 6 months after the implementation of the SmPC changes, and results will be compared with those obtained in DUS1. Evaluation of the impact of the risk minimisation measures will be conducted through the following variables according to the sections of the SmPC:

- **Indications:** Smoking status at the start date; number of patients with a visit to the general practitioner and/or to a specialist between 3 months and 4 months after the start date; number of patients discontinuing cilostazol between 3 months and 4 months after the start date
- **New contraindications:** Number of patients with a recorded diagnosis for unstable angina pectoris, myocardial infarction, or coronary intervention, within 6 months before the start date; number of patients with concurrent use of two or more platelet aggregation inhibitors at the start date and during follow-up

- Warnings and precautions: Patients with a history of arrhythmias, hypotension, or coronary heart disease recorded at any time before the start date will be followed to assess the rates of visits to general practitioners or specialists
- Posology: Reduction of daily dose to 100 mg will be assessed among patients who are prescribed a potentially interacting medication or a potent inhibitor of CYP3A4 or CYP2C19 during current use of cilostazol.

Use of cilostazol will be evaluated for the use in patients with diseases and conditions currently listed as contraindications in the SmPC that will be retained in the revised SmPC. These conditions are severe renal impairment, moderate to severe hepatic impairment, congestive heart failure, history of bleeding disorders, and history of arrhythmias.

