### **9.7.3 Use of Medications Potentially Interacting With Cilostazol**

Analysis Tables 10, 11, 12, 13, and 27: Use of medications potentially interacting with cilostazol will be assessed at the start date (Analysis Table 10), during current use of cilostazol (Analysis Table 11), during consecutive use of cilostazol (Analysis Table 12), and at any of these times (Analysis Table 13). The list of relevant medications potentially interacting with cilostazol is presented in Table 6 (Section 9.3.4) and protocol Annex 3. The number and percentage of concurrent users of each potentially interacting medication will be calculated by sex and age group (< 70 years, ≥ 70 years). Concurrent use of cilostazol and potent inhibitors of CYP3A4 and CYP2C19 will also be evaluated. Potent inhibitors are lansoprazole, fluvoxamine, nefazodone, ticlopidine, clarithromycin, troleandomycin, indinavir, ritonavir, nelfinavir, mibefradil, ketoconazole, and itraconazole. The distribution of users by the number of interacting medications received concurrently with cilostazol will be calculated (Analysis Table 27).

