### **9.7.5 Assessment of Changes to the Summary of Product Characteristics**

Analysis Tables 17, 18, and 26: The number and percentage of users by sex and age group (< 70 years, ≥ 70 years) will be calculated for the following conditions:

- Smoking: current, past, non-smoker (Analysis Table 17A)
- Number and percentage of users with at least one visit for any reason with a general practitioner or specialist between (a) 2 months and 4 months after the start date and (b) 1 month and 6 months after the start date, evaluated by the clinical review of a sample of patient profiles (Analysis Table 17B) and by diagnosis codes in all users (Analysis Table 17C). Analysis is restricted to patients who are current users of cilostazol at 3 months after the start date.
- Number and percentage of users with at least one visit for intermittent claudication with a general practitioner or specialist between (a) 2 months and 4 months after the start date and (b) 1 month and 6 months after the start date, evaluated by the clinical review of a sample of patient profiles (Analysis Table 17B) and by diagnosis codes in all users (Analysis Table 17C). Analysis is restricted to patients who are current users of cilostazol at 3 months after the start date.
- Discontinuation of cilostazol between 3 months and 4 months after the start date, evaluated using Kaplan-Meier survival curves (Analysis Table 17A and 26)

- Diagnosis within 6 months before the start date: unstable angina, myocardial infarction, or coronary intervention (Analysis Table 17A)
- Concurrent use of cilostazol and two or more platelet aggregation inhibitors (Analysis Table 17A)
- Reduction of daily dose of cilostazol from 200 mg to 100 mg among concurrent users of cilostazol and (a) potentially interacting medications (Analysis Table 18A) or (b) potent inhibitors of CYP3A4 or CYP2C19 (Analysis Table 18B) during continuous use of cilostazol

Analysis Table 19: Rates of visits to general practitioners and/or specialists among users at increased risk of serious cardiac events (patients with history of arrhythmias, coronary heart disease, or hypotension). Rates of visits per 100 person-years and 95% confidence intervals (CI) will be calculated for these patients and for those who are not considered at increased risk of serious cardiac events. Rate ratios and 95% CIs will be estimated comparing the rates in patients with increased risk with rates in patients without increased risk.

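### Analysis Table 18B rests on a closed list of 12 potent inhibitors that omits omeprazole, the only CYP2C19 inhibitor named in the SmPC posology text under evaluation, and the protocol gives no reason

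*Protocol*

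**What the plan says.** Table 7 of the protocol sets out the SmPC changes whose impact DUS2 is to assess. Its posology entry concerns patients who receive strong CYP3A4 inhibitors, for which it gives three drug classes as examples, or "medicines that strongly inhibit CYP2C19, e.g., omeprazole". Daily dose is the characteristic to be evaluated.

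Section 9.3.4.1 defines the potent-inhibitor group. Membership is set by two outside sources: "Potent inhibitors are those identified as such by the Indiana Classification" and by a US FDA website. The list is then closed: "Potent inhibitors are lansoprazole, fluvoxamine, nefazodone, ticlopidine, clarithromycin, troleandomycin, indinavir, ritonavir, nelfinavir, mibefradil, ketoconazole, and itraconazole". Section 9.7.3 repeats the same 12 drugs.

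Section 9.7.5 applies two groups to the dose-reduction analysis: "a) potentially interacting medications (Analysis Table 18A) or (b) potent inhibitors of CYP3A4 or CYP2C19 (Analysis Table 18B) during continuous use of cilostazol". The Abstract also names both groups: "prescribed a potentially interacting medication or a potent inhibitor of CYP3A4 or CYP2C19 during current use of cilostazol". For treatment initiation, Section 9.3.6 uses only the broad group: "Daily dose of cilostazol at the start date will be assessed among concurrent users of potentially interacting medications at the start date".

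**The concern.** DUS2 is meant to show whether prescribing changed after the SmPC was revised. For the posology change, the informative group is the patients to whom the quoted sentence applies. Table 18B looks designed to isolate that group, but its list leaves out the one individual drug that the sentence names. Lansoprazole is on the list, although Table 6 and Annex 3 mark both drugs as CYP2C19 substrate and inhibitor. The protocol does not explain the difference.

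What is at stake is interpretation. A dose-reduction percentage from 18B would be silent on patients whose only relevant drug is omeprazole. A percentage from 18A would mix in patients on drugs for which the sentence asks no change, so a low value there could be misread as failure of the measure. Table 1 records that the potent-inhibitor evaluation was added in version 2.3 at the regulator's request, so the regulator is likely to read 18B as the answer on strong inhibitors.

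**Working it through.** The protocol states no figure for this point, so the check compares lists.

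1. **Posology sentence (Table 7).** For CYP3A4 it names classes: several macrolides, azole antifungals and protease inhibitors. For CYP2C19 it names one drug, omeprazole.

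2. **Annex 3, counted by marking.** There are 67 drugs. Six are marked as CYP2C19 inhibitors: lansoprazole, omeprazole, fluoxetine, fluvoxamine, ticlopidine and ketoconazole. Fifteen are marked as CYP3A4 inhibitors. Two (fluvoxamine and ketoconazole) are in both sets, so there are 6 + 15 − 2 = 19 inhibitors. The other 67 − 19 = 48 are only substrates or inducers, such as amlodipine, simvastatin, atorvastatin, clopidogrel, carbamazepine and rifampin.

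3. **The 12-drug list against Annex 3.** All 12 drugs are in Annex 3. The list includes drugs from each CYP3A4 class in the sentence: clarithromycin and troleandomycin; ketoconazole and itraconazole; indinavir, ritonavir and nelfinavir. It holds 4 of the 6 CYP2C19 inhibitors and omits omeprazole and fluoxetine. With omeprazole added it would have 13 drugs and hold 5 of the 6.

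4. **Where omeprazole users appear.**

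| Output | Group | Omeprazole users included? | Matches the posology sentence? |
|---|---|---|---|
| 18B, dose reduction | 12 potent inhibitors | Only if also on a listed drug | No: named drug absent |
| 18A, dose reduction | Potentially interacting medications | Yes | No: also covers substrates and inducers |
| Start-date dose (9.3.6) | Potentially interacting medications | Yes | No, for the same reason |
| Tables 10–13 | Each interacting drug | Yes, individually | Counts use, not dose |

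5. **Size.** The documents do not give the prevalence of omeprazole or of the 12 drugs. Purely as an illustration, let a share o of users take omeprazole and a share p take a listed drug, independently. The share of the combined group seen by 18B is then p / [1 − (1 − o)(1 − p)].
   - o = 0.40, p = 0.02: 0.02 / 0.412 = 5%.
   - o = 0.10, p = 0.10: 0.10 / 0.19 = 53%.

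   The answer is driven by the assumed inputs, so no size is claimed.

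**The case against.** The best defence is that 18B follows a stated rule. The potent group is defined by two named outside classifications, not by the SmPC wording, and it supplements the broad analysis. Those sources are not available here, so it cannot be said that the list misapplies them. This stands: the criticism is an unexplained divergence between the classification and the label text, not a transcription error.

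A reader might infer that the posology evaluation misses omeprazole users altogether. The documents do not support that. These patients are in 18A and in the start-date dose measure, and their use is counted drug by drug in Tables 10–13. Omeprazole also has its own row in Table 5. 18B itself still covers much of what the sentence describes.

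The dilution argument has a limit too. The table shells are separate files and are not shown. If 18A reports dose reduction by drug, an omeprazole figure would already exist. Section 9.7.5 does not say that it does, and the drug-level reporting that Section 9.7.3 does promise concerns concurrent use.

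Finally, Table 7 is headed as proposed changes submitted in October 2012. Section 6.2 dates approval to May 2013, and the approved text is not reproduced. The exact target set should therefore be taken from the approved SmPC.

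**Conclusion.** The mismatch holds. Sections 9.3.4.1 and 9.7.3 fix a potent-inhibitor list without the only CYP2C19 inhibitor that Table 7 names, and give no reason. As described, 18B is too narrow for the quoted sentence, while 18A and the start-date measure are too broad, so no dose-reduction group corresponds to it.

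The consequence is limited. The study is descriptive, and the omission affects no cohort definition or study size. Omeprazole use is already ascertained. It would be tempting to say that 18B sees only a small fraction of the target patients, but no usage data in the documents support any fraction. The conclusion assumes that the approved SmPC kept omeprazole as its example and that the unseen shell for 18A does not already report dose reduction by drug. It takes no position on whether omeprazole is pharmacologically a strong inhibitor or on any dose. The point is only that the analysis group and the text it evaluates should agree, or that the difference should be explained.

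**What to change.** Reconcile Sections 9.3.4.1 and 9.7.3 with the posology entry in Table 7:

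- Report 18B for the 12 listed drugs plus omeprazole, adding any other inhibitor that the approved SmPC names, or show omeprazole as a separate row.
- Keep the 12-drug classification-based list as its own row, and say in one sentence why it differs from the label text.
- Use the same grouping for the potent-inhibitor rows on concurrent use (Section 9.7.3) and for daily dose at the start date (Section 9.3.6).
- State that 18A describes broad interacting-drug use and is not a measure of compliance with the posology sentence.

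No new data are needed, because Section 9.3.4 already ascertains every Annex 3 drug, including omeprazole. The cost is a small rerun for comparability in DUS1. That is not free: Section 6.1 reports four DUS1 databases complete by 30 January 2015 and the final report due in April 2015, so finished analyses at several centres would have to be reopened.
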